### **Data analysis:**

Each variable was inspected for extreme outliers (i.e., data points that fell more than 4 standard deviations [SD] away from the mean) using summary statistics and box plots. An extreme outlier was excluded from the final analysis. Normality of the variables was determined based on skewness and kurtosis. Number that is greater than +1 or lower than -1 indicate a substantially skewed distribution. For kurtosis, if the number is greater than +1, the distribution is too peaked and less than -1 indicates a distribution that is too flat. If the distribution was found to deviate from normality, non-parametric statistical analysis was conducted.

Descriptive statistics described the study sample for age, sex, height, weight, race, current medication, education level, exercise level, DHI, ABC, history of falls, MoCA and HI- MoCA. To determine if the groups are similar with respect to background measures and demographics a comparison of the three groups Normal hearing, Mild BHL and > Moderate BHL (moderate, moderately-severe, severe and profound) was done using one-way analysis of variance (ANOVA) or non-parametric Kruskal-Wallis Test for continuous measures and Chi-square analyses for categorical measures (e.g., gender).

For Aim #1: Compare single task (=ST) gait parameters between individuals age and education-matched with Mild BHL, > Moderate BHL and controls with Normal hearing and Aim #3: Compare the effect of a cognitive task on gait parameters (=DT) between age and education-matched people with Mild BHL, > Moderate BHL and control with Normal hearing: For the primary outcome measure, gait speed and its variability, and secondary outcome measures (stride length, stride time and their variability) during the 1-min walk, a mixed model repeated measures (RM)- ANOVA was conducted with 1 within-factor (task) of 2 levels (ST and DT ['subtraction 3']) and 1 between factor (group) of 3 levels (Normal hearing, Mild BHL, Moderate BHL). When the distributions were found to deviate from normality the Kruskal-Wallis' test was conducted for a between-group comparison and the Wilcoxon signed-rank test for a within-group comparison. Since I had a significant difference with age, I adjusted for age the ANOVA comparison.

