Partial Eta Square (PET) Effect Size was reported for each main effect and interaction (small effect, PET  $\geq 0.08$ ; middle effect, PET  $\geq 0.20$ ; and high effect, PET  $\geq 0.32$ ). P-values with a value of  $p < 0.05$  were considered statistically significant. Bonferroni corrections were applied to post hoc comparisons as applicable.

For Aim #2: Compare cognitive function (i.e., the Neurocognitive Index) between individuals age and education-matched with Mild BHL, > Moderate BHL and controls with Normal hearing. One way ANOVA (or non-parametric Kruskal-Wallis Test) was used to compare the Neurocognitive Index between the three groups. Moreover, one way ANOVA (or non-parametric Kruskal-Wallis Test) was used to compare the secondary outcome measures, i.e., Composite Memory, Verbal Memory, Visual Memory, EF, Cognitive Flexibility, Complex RT, Working Memory and Sustained Attention and the cognitive ST and DT performance. I used one-way ANOVA with the dependent variable, the cognitive domain (Neurocognitive Index or any of the secondary outcome measures), and group as independent variable. For the raw scores I used the ACNOVA to adjust for age since we had significant age difference and these results do not present an age-matched score. Cohen's d effect size was calculated per comparison and was defined 'small' effect size as  $d = 0.2$ , 'medium' effect size as  $d = 0.5$  and a 'large' effect size as  $d = 0.8$ .

For Aim #4: Explore whether cognitive performance (i.e., the Neurocognitive Index) is correlated with DTC per group. One way ANOVA (or non-parametric Kruskal-Wallis Test) was used to compare the DTC between the three groups. Correlations between the cognitive domains and DTC were assessed using Pearson's correlation (or its non-parametric equivalent Spearman's, if the distributions are found to deviate from normality) for continuous variables. Pearson's correlation for each comparison was defined as 'little to none' for  $r = 0-0.24$ , 'fair' for  $r = 0.25-0.49$ , 'moderate to good' for  $r = 0.50-0.74$  and 'good to excellent' for  $r = 0.75-1.00$ . SPSS version 27 IBM (NY, US) was used for all statistical analysis.

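### Nothing controls error across the two primary gait outcomes (up to 9.75% per effect) or across the secondary scores and correlations (up to 43% in Aim 2, 75% in Aim 4)

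*Combined protocol and SAP*

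**What the plan says.** All of this is in the Data analysis section of the combined protocol and SAP.

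- **Threshold.** "P-values with a value of $p < 0.05$ were considered statistically significant". No other threshold is given for any aim.
- **Correction.** "Bonferroni corrections were applied to post hoc comparisons as applicable". No adjustment across outcomes, effects or correlations is described, and no testing hierarchy.
- **Aims 1 and 3.** One repeated-measures ANOVA (three groups, two tasks) serves both aims: "For the primary outcome measure, gait speed and its variability, and secondary outcome measures (stride length, stride time and their variability". That makes two primary and four secondary gait measures. For each model, "Effect Size was reported for each main effect and interaction".
- **Aim 2.** A one-way ANOVA "was used to compare the Neurocognitive Index between the three groups". The same test is then applied to a list labelled secondary: "Composite Memory, Verbal Memory, Visual Memory, EF, Cognitive Flexibility, Complex RT, Working Memory and Sustained Attention and the cognitive ST and DT performance".
- **Aim 4.** The aim is "Explore whether cognitive performance (i.e., the Neurocognitive Index) is correlated with DTC per group". The analysis is wider than the Index: "Correlations between the cognitive domains and DTC were assessed using Pearson's correlation". The correlations are also graded by the size of r.
- **Timing.** The section is in the past tense. It says that age was added to the ANOVA because the groups were found to differ significantly in age.

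**The concern.** The primary outcome is named in the singular but consists of two measures. Each is tested in a model that yields several effects, and the plan does not say whether one or both must be significant, or on which effect. An author who follows it may claim a primary finding if either measure falls below 0.05.

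The Bonferroni rule does not help here. It governs comparisons between groups after an overall test, not the number of overall tests. The secondary cognitive scores and the per-group correlations face the same 0.05 threshold, with no statement that they are unadjusted. At stake is interpretation: a lone positive subscale or correlation could be reported as an effect of hearing loss when one such result by chance would not be surprising.

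**Working it through.** The documents give no sample size, power or family-wise error rate, so there is no stated figure to reproduce.

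**Counts**

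- Primary gait outcomes: 2 (gait speed, its variability). With stride length, stride time and the variability of each: 6.
- Effects per gait model: 3 (group, task, interaction). Two of these, group and interaction, bear on the between-group aims.
- Aim 2: the Index plus 8 named scores = 9. Adding cognitive single-task and dual-task performance gives at least 11.
- Aim 4: under Aim 2 the plan uses the term cognitive domain for the Index or any secondary score. Nine scores × 3 groups = 27 correlations, assuming one DTC measure. The 27 is derived, not stated. The between-group ANOVA of DTC is not counted.

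**Formula.** If no effect exists and k tests are independent, the chance of at least one p < 0.05 is 1 − 0.95^k.

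**Correlated outcomes.** Because outcomes from the same people are correlated, the formula was supplemented by simulation: 4,000 runs, 15 or 30 per group, common correlation between outcomes from 0.3 to 0.9. These settings are assumptions; the documents give none of them. Monte Carlo standard error is at most √(0.5 × 0.5 / 4000) = 0.8 percentage points.

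| Family | k | Independent | Correlated |
|---|---|---|---|
| Two primaries, one effect | 2 | 1 − 0.95² = 9.75% | about 6–10% |
| Two primaries, group and interaction | 4 | 1 − 0.95⁴ = 18.5% | 16–19%* |
| Six gait measures, one effect | 6 | 1 − 0.95⁶ = 26.5% | about 10–25% |
| Aim 2, Index and eight scores | 9 | 1 − 0.95⁹ = 37.0% | about 12–34% |
| Aim 2, with single- and dual-task counting | 11 | 1 − 0.95¹¹ = 43.1% | about 13–40% |
| Aim 4 correlations | 27 | 1 − 0.95²⁷ = 75.0% | about 33–71% |

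*Separate simulation with 20 per group, single-/dual-task correlation 0.8 and outcome correlation 0 to 0.7, all assumed.

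In Aim 4 the expected number of false positives is 27 × 0.05 = 1.35. The chance of at least one stays above 50% up to a correlation of 0.7 between the scores (about 51–71% for 0.3 to 0.7) and falls to about 33% at 0.9.

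**If Aim 4 is read narrowly.** The Index against one DTC measure in three groups is 3 tests: 1 − 0.95³ = 14.3%.

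**With adjustment.** Holm starts at 0.05/2 = 0.025 for the two primaries and at 0.05/3 = 0.0167 for three correlations. With independent tests the family error is 1 − 0.975² = 4.9% and 1 − (1 − 0.0167)³ = 4.9%.

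**The case against.** The strongest reply is that the plan has more structure than the bare test count suggests. It labels primary and secondary outcomes for gait. Aim 2 equates cognitive function with the Index and tests it once, so that lead test runs at 5%. Aim 4 is introduced as exploration and grades correlations by size as well as by p-value. The document is titled a pilot study, and formal control over every secondary measure in a pilot is partly a matter of taste. The plan also promises no family-wise rate; 0.05 is a per-test threshold.

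All of that stands, and it rules out several stronger readings:

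- A reader might infer that a chance significant result is likely within every aim. Only Aim 4 passes 50%, and not when the scores are very highly correlated. The primaries are at about 10% per effect, and Aim 2 is below 50% even if its tests are independent.
- A reader might infer that no aim keeps a 5% error rate. The single test of the Index does.
- A reader might multiply 27 by two or six DTC measures, to 54 or 162. The documents do not say how many there are.
- A reader might infer from the past tense that the outcome hierarchy was chosen after the results were known. The text shows only that the age adjustment was driven by the data.

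The 18.5% figure also pools two aims. If each aim is tied to one effect, 9.75% is the ceiling per aim.

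The reply does not supply a decision rule for the two primaries, or a statement that secondary scores and correlations below 0.05 are unadjusted.

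**Conclusion.** The point holds as a gap in the decision rule for the primary outcome and in the labelling of the other tests. Following the plan as written, the false-positive risk across the two primary gait outcomes is up to 9.75% per effect, or up to 18.5% if group and interaction are pooled over Aims 1 and 3. Outside the primaries it is up to 37–43% over the Aim 2 scores and up to 75% over 27 Aim 4 correlations.

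These are upper figures. They assume that no true effect exists, that tests are independent, that the single stated threshold applies to all four aims, and that there is one DTC measure. The simulated ranges depend on assumed sample sizes and correlations. The Aim 2 and Aim 4 figures concern secondary and exploratory results, so they bear on how those results may be described and do not undermine the lead test of the Index.

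**What to change.** - **Aims 1 and 3.** Name one effect per aim, as the aims' own wording implies: for Aim 1 the group comparison of single-task gait, for Aim 3 the group-by-task interaction. The group main effect of the repeated-measures model averages over both tasks, so it is not quite the Aim 1 question. Within each aim, apply Holm to gait speed and its variability.
- **No fixed sequence.** Testing gait speed first and its variability second would protect the error rate only if the order had been set in advance. This text was written after data were seen, so an order chosen now cannot be presented as prespecified. Holm needs no order.
- **Aim 2.** Keep the Neurocognitive Index as the only test at 0.05.
- **Aim 4.** Limit significance statements to the Index against gait-speed DTC, Holm-adjusted across the three groups.
- **Everything else.** Report the other gait measures, cognitive scores and correlations as exploratory estimates with confidence intervals and do not call them significant, or apply Benjamini-Hochberg within each family and say so.

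The cost is SAP wording and table labels; no new data are needed. Under Holm the smaller of the two primary p-values must fall below 0.025 before the other is tested at 0.05, so a single primary result between 0.025 and 0.05 no longer counts. Some secondary results can no longer be called significant. Control is within each aim; Aims 1 and 3 taken together could still reach 1 − 0.95² = 9.75%, which is acceptable if they are reported as separate questions.

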13. TMT A & B
14. Practice trial: Walking back and forth the corridor

15. Randomized Trial- each trial will be done 1 time (without hearing aid):

1. Single cognitive task sub1 - [Baseline] while sitting (serial subtraction of 1) + record with phone
2. Single cognitive task sub3 - [Baseline] while sitting (serial subtraction of 3) + record with phone
3. Single motor – [Baseline] Walking on the ground for 1 min a 10 m long corridor – recording with a stopwatch
4. Dual task cognitive sub1 (DT\_sub1) - serial subtraction of 1 + #3 - recorded with stopwatch + record with phone
5. Dual task cognitive sub3 (DT\_sub3) - serial subtraction of 3 + #3 - recorded with stopwatch + record with phone

Using REDCAP:

16. DEMOGRAPHIC questionnaire (descriptive)
17. ABC – In healthy young adults ask: “have you never had any concern regarding: balance?” – if yes- fill up the questionnaire. (descriptive)

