### **Gait:**

“Walk straight ahead at your comfortable speed until you see the mark on the floor and then turn and walk straight ahead to the opposite direction. Keep walking until I will tell you to stop. The total time for walking is 1 min. If you lose your balance do whatever feels safe to stay steady. One of the researchers is going to walk next to you to prevent any fall”.

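### Aim 1 (single-task gait) is tested only inside the two-task model, so under a classical RM-ANOVA a missing serial-3 walk would also remove that participant's single-task walk

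*Combined protocol and SAP*

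**What the plan says.** The Data analysis section states Aim 1 as a single-task question: "Compare single task (=ST) gait parameters between individuals age and education-matched with Mild BHL, > Moderate BHL and controls with Normal hearing". It then treats Aims 1 and 3 together. For gait speed, stride length, stride time and their variability, "a mixed model repeated measures (RM)- ANOVA was conducted with 1 within-factor (task) of 2 levels (ST and DT ['subtraction 3", with hearing group (three levels) as the between factor and an adjustment for age. No one-way comparison of ST gait is listed, although one-way ANOVA is specified for Aims 2 and 4.

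Other parts of the documents bear on this:

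- Step 15 of the pilot protocol, on the walking and counting tasks: "each trial will be done 1 time".
- The gait instruction: "If you lose your balance do whatever feels safe to stay steady". The same sentence stands in the single-task script and in both dual-task scripts.
- Outliers: points more than 4 SD from the mean are excluded. The text does not say whether the value or the whole participant goes.
- Effect sizes: "Partial Eta Square (PET) Effect Size was reported for each main effect and interaction".
- Software: "SPSS version 27 IBM (NY, US) was used for all statistical analysis". The SPSS procedure is not named.
- Non-normal variables: "When the distributions were found to deviate from normality the Kruskal-Wallis' test was conducted for a between-group comparison", with Wilcoxon signed-rank within groups. The text does not say which gait value enters the between-group test.

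Nothing is said about a walk that is stopped, unusable or missing, or about how many participants had each walk.

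**The concern.** A classical repeated-measures ANOVA needs a value at every level of the within factor. With two levels, ST and serial-3 dual task (DT), a participant who lacks the DT value contributes nothing, and a valid ST walk is discarded with the missing one. Aim 3 compares the two tasks, so needing both walks is understandable there. Aim 1 needs only the ST walk.

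If those without a usable DT value differ in ST gait from the rest of their group, the ST group means come from a selected set and the group difference in a primary outcome can be distorted. Even without selection, usable observations are lost in a pilot study. The reader also cannot tell who is in the Aim 1 analysis. In addition, the model's group main effect averages over ST and DT, so the Aim 1 comparison has to be a contrast at ST, and the plan does not write that contrast down.

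**Working it through.** The documents give no sample size, missing-walk rate or completer count, so there is no figure of the plan's own to reproduce. The check has three parts.

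**1. Which procedure is meant?** The text names an RM-ANOVA with one within and one between factor, partial eta squared for every effect, and SPSS 27. It names no random effect, covariance structure or estimation method. Together these fit GLM Repeated Measures, where the term mixed means between-within. GLM Repeated Measures uses complete pairs only. A likelihood mixed model would keep a lone ST value. The deletion is therefore inferred from the wording and not stated.

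**2. How could a DT value be absent?** Each walk is done once, so a failed serial-3 walk has no planned replacement. The outlier rule could also remove one member of a pair, if it removes the value and not the person. The largest possible standardised distance in a sample of n is (n − 1)/√n:

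- n = 17: 16/√17 = 3.88, so no value can exceed 4 SD.
- n = 18: 17/√18 = 4.01, so exclusion is just possible.

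The outlier route thus needs at least 18 values in the set being screened.

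**3. Illustrative size (all inputs assumed).** Let m be the share of one group without a usable DT value and ρ the correlation between ST gait and the ability to complete the DT walk. Under normality, the shift in that group's completers' ST mean, in SD units, is

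shift = ρ × φ(z_m)/(1 − m).

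At m = 10%: φ(z_m)/(1 − m) = 0.1755/0.90 = 0.195. Multiplying by 0.3 and 0.7 gives about 0.06 and 0.14. The full set, from unrounded values, is:

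| m | ρ = 0 | ρ = 0.3 | ρ = 0.5 | ρ = 0.7 |
|---|---|---|---|---|
| 0 | 0 | 0 | 0 | 0 |
| 5% | 0 | 0.033 | 0.054 | 0.076 |
| 10% | 0 | 0.058 | 0.097 | 0.136 |
| 20% | 0 | 0.105 | 0.175 | 0.245 |

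A simulation supports the formula. It assumed 20 per group, ST–DT correlation 0.8, a true ST difference of −0.50 SD, 15% loss in one group, ρ = 0.5 and no age effect. Over 2000 runs the mean ST difference was −0.37 from complete pairs and −0.50 from all ST walks. The formula gives 0.137 for this case, and −0.50 + 0.137 = −0.36, which agrees. In the first 200 runs a random-intercept mixed model and the all-ST comparison both gave −0.48, so the mixed model recovers the ST contrast that complete pairs lose.

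**The case against.** The strongest reply is that the problem may never have arisen. The walk lasts one minute at comfortable speed with a researcher alongside, and participants are screened for vision, foot sensation and dizziness. Gait is recorded by worn sensors, so poor or abandoned subtraction need not cost the gait data. The balance sentence does not say that a walk ends, and it appears in the ST script too, so it does not single out the DT walk. The outlier rule is two-sided and applies variable by variable, so it need not remove the slowest walkers. All of this stands: no missing serial-3 walk is documented.

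A reader might go further than the text allows in four ways.

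- **That Aim 1 was in fact estimated on dual-task completers.** This needs both the GLM reading and at least one missing DT value. The first is likely but unstated, and the second is not shown.
- **That losses fall on the slowest walkers with > Moderate BHL and shrink the group difference.** The documents give no loss rate by group and no link between loss and gait. Shifts of 0.11, 0.20 and 0.35 SD at 5%, 10% and 20% loss require ρ = 1, with exactly the slowest walkers of one group lost. They are a ceiling and not an estimate.
- **That the Kruskal-Wallis branch keeps the ST value, so the analysed set changes with the normality result.** It would if run on ST values alone, but the plan does not say what enters that test.
- **That the walk listed as "Dual task cognitive sub1" is never analysed for gait.** Aim 4 compares dual-task cost without saying which dual task it uses, so this is not established.

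What the objection does not answer is that Aim 1 has no parametric analysis of its own and that the plan has no rule for a missing walk.

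**Conclusion.** The point holds in conditional form. Aim 1 is tested parametrically only within the ST/serial-3 model. If that model is SPSS GLM Repeated Measures, anyone without a usable serial-3 value also leaves the ST comparison. Bias is a risk of unknown size and direction. It is zero with complete pairs, and zero if loss is unrelated to ST gait. For scale only, 10% loss confined to one group gives a shift of about 0.06 to 0.14 SD in that group's ST mean, assuming normal ST gait and a correlation of 0.3 to 0.7. Neither the loss rate nor the correlation comes from the documents. The change is worth making because it gives Aim 1 an explicit ST contrast, keeps every ST walk, and should closely match the planned analysis when no walk is missing.

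**What to change.** - **Aim 1:** compare ST gait between the three groups in everyone with a usable ST walk. Use either an age-adjusted one-way model or the group contrast at ST from a likelihood mixed model (SPSS MIXED: task, group, task × group and age, with within-participant correlation).
- **Aim 3:** use the same mixed model on all available ST and serial-3 walks, and test the task × group term. For a participant without a DT value, this assumes the loss is explained by the observed ST value, group and age. A random intercept alone also assumes equal variance in the two tasks; an unstructured two-by-two covariance avoids that.
- **Reporting:** name the SPSS procedure, give the number of usable walks by task and group, and say whether an outlier exclusion removes the value or the participant. If no walk was missing or excluded, one sentence saying so settles the selection question, leaving only the explicit ST contrast to be added.

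The cost is small: revised analysis text and a change of procedure, with no new data. Because the section is written in the past tense, the gait models would probably have to be rerun. MIXED does not give partial eta squared, so report adjusted mean differences with confidence intervals, or keep partial eta squared from a completers-only run labelled as such. Adding the serial-1 dual-task walk as a third task level is optional and not part of this fix.

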### **Gait Serial Subtraction 1**

“Walk straight ahead at your comfortable speed while counting backwards out loud in jumps of 1 from a number that I will tell. Start from the next number. For example, if I say 557, you start: 556, 555 and so on. When you see the mark on the floor you turn and walk straight ahead to the opposite direction. Keep walking and counting until I will tell you to stop. The total time for walking is 1 min. If you lose your balance do whatever feels safe to stay steady. One of the researchers is going to walk next to you to prevent any fall”.

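### The gait analysis omits the collected walk with subtraction by 1, so a group difference in dual-task cost cannot be traced to arithmetic load rather than other costs of counting aloud

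*Combined protocol and SAP*

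**What the plan says.** Aim #3, in the Data analysis section, is to "Compare the effect of a cognitive task on gait parameters (=DT") between the hearing groups. The model for Aims #1 and #3 has "1 within-factor (task) of 2 levels (ST and DT ['subtraction 3" and "1 between factor (group) of 3 levels (Normal hearing, Mild BHL, Moderate BHL", and the comparison is adjusted for age. If normality fails, Kruskal-Wallis is used between groups and Wilcoxon signed-rank within groups.

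Step 15 of the protocol collects three one-minute walks, each done once, in randomised order and without hearing aids:

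- a single-task walk, whose script (Gait) begins "Walk straight ahead at your comfortable speed until you see the mark on the floor" and asks for no counting;
- "Dual task cognitive sub1 (DT\_sub1) - serial subtraction of 1 + #3 - recorded with stopwatch + record with phone";
- the same with "serial subtraction of 3 + #3 - recorded with stopwatch + record with phone".

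The scripts for both counting walks require counting out loud. The script under Gait Serial Subtraction 1 opens "Walk straight ahead at your comfortable speed while counting backwards out loud in jumps of 1 from a number that I will tell". The script under Gait Serial Subtraction 3 opens with the same words, including the step of 1, although its worked example goes down in threes.

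Two other analyses use dual-task data without naming a subtraction level. Aim #2 compares cognitive performance in the single and dual tasks, which is not a gait outcome. Aim #4 uses DTC, which is not defined.

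**The concern.** The planned contrast changes two things at once. Compared with the single-task walk, the subtraction-3 walk adds continuous speech and adds arithmetic. A group-by-task interaction is naturally read as hearing loss raising the cognitive cost of walking. If talking while walking costs the groups different amounts, that difference enters the same interaction and cannot be told apart from load.

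The study already holds a condition that bears on this. The subtraction-1 walk uses the same course, duration and spoken mode with lighter arithmetic. Leaving it out, with no reason given, means the report cannot say whether a group difference grows with arithmetic load. It also leaves a collected condition unreported. The ambiguity may carry into Aim #4, depending on how DTC is calculated.

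**Working it through.** The plan gives no sample size, gait values or standard deviations, so there is no figure to reproduce. The check is what each set of conditions can estimate.

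**Definitions.** ST is the single-task walk; DT1 and DT3 are the walks with subtraction by 1 and by 3. A is the change from ST to DT1: speaking aloud plus whatever load subtraction by 1 carries. L is the further change from DT1 to DT3.

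**Planned analysis.** DT3 − ST = A + L. That is one contrast for two unknowns (rank 1), so A and L cannot be separated.

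**With DT1 included.** DT1 − ST = A and DT3 − DT1 = L. That is rank 2, so L can be estimated.

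**Between groups g and h.** The planned interaction compares (A + L) across groups:

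(A_g − A_h) + (L_g − L_h).

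If A is equal in all groups, the first term is zero and the planned interaction reflects L alone. The ambiguity exists only if A differs by group.

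**Illustration (all speeds assumed).** Take ST = 1.20 m/s and DT3 = 1.05 m/s, a total slowing of 0.15 m/s. The share present at DT1 is (1.20 − DT1) / 0.15.

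| DT1 (m/s) | Share at DT1 | DT1 to DT3 slowing | ST to DT3 slowing |
|---|---|---|---|
| 1.17 | 0.03/0.15 = 20% | 0.12 | 0.15 |
| 1.12 | 0.08/0.15 = 53% | 0.07 | 0.15 |
| 1.08 | 0.12/0.15 = 80% | 0.03 | 0.15 |

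The planned contrast is 0.15 m/s in every row; only the DT1 to DT3 contrast changes.

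**Precision of the added contrast.** If the walks have equal variance s² and equal pairwise correlation r, each paired difference has variance 2s²(1 − r), so the two contrasts have the same standard error. For the main effect of task, matching the power of ST versus DT3 then needs (0.15/d)² times the sample: (0.15/0.12)² = 1.6, (0.15/0.07)² = 4.6 and (0.15/0.03)² = 25. The added contrast can therefore be much weaker.

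**Why not a three-level task factor in the primary model.** With three groups, the group-by-task degrees of freedom go from (2 − 1)(3 − 1) = 2 to (3 − 1)(3 − 1) = 4, so the omnibus interaction no longer tests the primary contrast. Pairwise task contrasts go from 1 to 3, with a Bonferroni level of 0.05/3 = 0.0167. The Wilcoxon signed-rank fallback handles two conditions, not three.

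**The case against.** The strongest reply is that the analysis matches its aim. Aim #3 asks about the effect of a cognitive task on gait, and ST versus DT3 is that comparison. The documents nowhere claim to isolate arithmetic load from speech. This stands: a reader might infer that Aim #3 goes unanswered, and it does not.

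Second, the protocol labels subtraction by 1 a cognitive dual task, not a speech control. A reader might infer that adding it would fully separate load from counting aloud. It would not: A still mixes speech with light load. The scripts also set no counting rate, so the amount spoken may differ between the two walks. Step 11 lists subtraction by 3, but not by 1, in the TUG trials done beforehand, and that practice may shrink the difference between the walks.

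Third, a speaking cost common to all groups cancels in the interaction. A reader might infer that the planned interaction is biased. The documents show only that hearing aids are removed (step 7) and stay off in step 15; they give no evidence that the cost of talking differs by hearing group.

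Fourth, it is not certain that the subtraction-1 gait data go unused, because DTC in Aim #4 is undefined. What can be said is that no gait analysis names them.

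These points limit the concern without removing it. A graded-load contrast tells more about the meaning of a group difference than no such contrast, even when separation is partial.

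**Conclusion.** The point holds as a low-cost improvement to interpretation; it is not a fault in the primary comparison. ST versus DT3 is a valid overall dual-task effect. By itself it cannot show whether a group difference reflects added arithmetic load or other costs of counting aloud that vary with hearing. The size of that second component is unknown. The 20% to 80% range rests wholly on assumed speeds and shows only that the planned contrast cannot distinguish these cases.

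A reader might also conclude that a group difference should be credited to cognitive load only if it appears between the two counting walks. The documents do not support that rule. Subtraction by 1 carries load of its own, so a real load effect could already be present there, and in a pilot with no stated sample size a null result on a small contrast says little. A group difference in DT3 − DT1 supports a load effect; its absence is not evidence against one.

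This reading assumes that the two counting walks really differed in load, which the subtraction-3 script leaves unclear.

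**What to change.** 1. First reconcile the Gait Serial Subtraction 3 script, whose stated step is 1 and whose example is in threes, and record what participants were actually told.
2. Keep the two-level ST versus DT3 repeated-measures ANOVA as the primary gait analysis.
3. Add a secondary DT3 versus DT1 contrast with its group interaction, adjusted for age in the same way. This is equivalent to an age-adjusted comparison of the per-participant DT3 − DT1 difference across the three groups.
4. If normality fails, compare that difference between groups by Kruskal-Wallis, with Wilcoxon signed-rank within group. As in the existing fallback, the age adjustment is then lost and this should be said.
5. Report gait and DTC for subtraction by 1 beside subtraction by 3, and define DTC in Aim #4, including its subtraction level.
6. State the one-sided reading given in the conclusion above: presence supports load, absence does not refute it.
7. The Data analysis section is written in the past tense. If results have been seen, label the contrast post hoc, and say why the condition was not analysed before.

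The cost is some analysis wording, a little more output and one more secondary contrast. No new data are needed and the primary test is unchanged. The limit is that speech and load are only partly separated.
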